6.3.4 Recruitment, Enrollment and Retention

How participants will be identified:

- To identify infants at-risk for neurodevelopmental disorders, we will use a population-screening method based on birth records in North Carolina, mailing postcards to families of children in this age range within our catchment area; we will supplement recruitment by distributing postcards/flyers through physician's offices, public health clinics, and childcare programs, and via email and listserv announcements; we also will reach out to families of young children via social media groups that include parents of young children in our catchment area, and via booths at family-oriented local

fairs/festivals. All of these will be directed at providing parents with an opportunity to complete the FYIv3.1 for their 11- to 16-month-old infants.

How and where participants will be recruited:

- Participants will be recruited throughout the central region of North Carolina through two primary sources: (a) state birth registries (NC Vital records; 6 counties within 90 miles of Chapel Hill including Orange, Durham, Chatham, Alamance, Guilford, and Wake), and (b) primary care well-baby clinics — either through local pediatric practices or county health clinics, in rural and urban areas that represent wide demographics. Our team has experience and success with these methods over the past 15 years through other research studies. Families identified through birth registries will receive an informational postcard (via postal mail) asking the parent of the infant to complete the survey (FYI) online or to request a paper form, and return to the project's PO Box. Families identified through pediatric practices and health clinics will be given an informational postcard at the time of their well-baby visits by office staff at those clinics. They may also fill the FYI out online or as a paper form and return to the project's PO Box. Filling out the form constitutes consent for the initial screening (based on our previous IRB approved procedures). For recruitment via listservs, the listserv message will include a link to the online FYIv3.1b as well as contact information for the project (email, phone) through which parents can request a hard copy of the FYI. Finally, for booths at local family-oriented fairs and festivals,

Likelihood we will have access to the targeted number of participants:

- Based on previous studies with similar methodologies and catchment areas, we estimate that the families of 32,000 infants will have the opportunity to complete the FYIv3.1 over the course of the project, with an overall return rate of ~15%, yielding 4800 completed FYIs. We anticipate that 5% of these infants (N=240) will score at risk on the FYI (i.e., risk scores \geq 95th %ile based on the FYIv3.1 normative data). Of those, 35% will be eligible for the assessment phase of the study and agree to the developmental assessment at UNC (N=84), and 57% of these will meet full inclusion criteria (N=49). Of those, 90% will consent to randomization, yielding approximately 44-45 families to randomize into the intervention study. The inclusion enrollment table provides the breakdown by sex and ethnicity given the North Carolina demographics, adjusted for expected attrition for non-English speaking families (i.e., we have reduced Hispanic enrollment by 1/3 of census figures). [NOTE: Current census demographics are: 64.7% White (not Hispanic); 22.0% Black/African American; 2.5% Asian; 8.7% Hispanic/Latino*; 2.0% More than one race; 0.1% Native Hawaiian/Pacific Islander; 1.5% American Indian/Alaska Native. Births in the 6 county catchment area numbered 26,814 in 2014 and birth rates have increased since then. We will broaden the catchment area to adjacent urban areas (e.g., Winston-Salem; Fayetteville) as needed to yield the target sample.]

Protection of privacy of potential subjects during recruitment:

- Postcards about the study will be mailed to families on a one-time basis when the children are between 11 and 16 months of age. These cards will be sent to families based on birth records alone, with no prior knowledge of how the infants will score on

the FYI. The postcards will give a web address to which parents can go to complete the FYIv3.1; in addition, families will be provided an email address and phone number, either of which can be used to request that a hard copy of the FYIv3.1 be mailed to them. The FYIs will be returned by parents, unscored, in a postage-paid self-addressed envelope, or will be completed online. FYIs will also be available at pediatric practices and health clinics along with postage-paid self-addressed envelopes. The FYIs will be identified with the potential participants' assigned ID numbers rather than with names. Agreement to subsequent contact and contact information (names, addresses, phone numbers) will be collected on a separate form from the FYI. This information will be stored in a separate file from the FYI results, and linked via the participant ID number. For any FYIs flagged due to a child meeting the predefined criteria (risk scores at or above the 95th %ile), the Project Coordinator will retrieve the contact information using the participant ID and initiate contact with the family by phone. In the event that the family does not answer and the call goes to voicemail, the Project Coordinator will leave a message that she has called along with her phone number, but will not leave any information pertaining to the FYI results.

How potential participants will be contacted:

- Completed FYIs will be scored and screened for risk status. Infants who score ≥ 95 th %ile risk score will be flagged, and those families will receive a phone call informing them of the results of the screening (by a qualified/trained project coordinator), and screening the child and family for additional inclusion and exclusion criteria if they are interested in potentially participating in the study. Those who have continued to meet eligibility criteria that can be assessed through the FYIv3.1b and the phone call will be invited for a more comprehensive baseline assessment. A maximum of 4 attempts will be made to contact a family: an initial phone call, a follow-up phone call if there is no response to the initial call after one week, an email (if the parents provided an email address in their contact information), and finally a mailed letter. The goal in the first three attempts will be to have a phone conversation with one of the child's parents, to inform them about the child's score on the FYI, to offer resource information about the public early intervention program, and to determine whether the child/family are eligible to participate in the Baseline assessment. If we do not get a response to the first three attempts, we will include information about the child's screening results and contact information for the regional Child Development Service Agency that would serve the family in the letter, as well as contact information for the project should the parents wish to discuss the screening results or potentially consider consenting to an initial evaluation at that point. If we get no response from the parents after these 4 attempts, we will assume the parents have declined enrollment in the study.

Who will do the recruiting:

- Recruitment materials (flyers, mailings ,etc.) will be prepared by study staff and volunteers, who also will distribute recruitment materials to health care facilities, childcare programs, on social media, and at local fairs/festivities. At local fairs and festivals, study staff will use tablet computers to provide parents of children in the age range access to an electronic version of the FYIv3.1b. Phone contacts with parents of children who score at-risk for the FYIv3.1, phone screening for exclusion criteria, explanation of the study, mailing of study information and consent forms, and the in-

person informed consent process will be the responsibility of the Project Coordinator.

6.3.5 Study Visits

1. The baseline assessment visit will take place in the study's office in Carrboro, NC, as soon after the phone call and will last approximately 1 1/2 to 2 hours. Parents will also complete a questionnaire requiring an additional 15 minutes, at the location of their choice. The following assessments will be completed:

- Parent-infant Interaction session - 20 minutes (Videos of this session will be used to measure Dyadic Engagement, Parent Responsiveness to Sensory Reactivity Cues, Parent Responsiveness to Prelinguistic Cues, and Infant Intentional Communication)
- Child-Directed Speech Paradigm - 10 minutes (Will be used to collect respiratory sinus arrhythmia and skin conductance level measures).
- Mullen Scales of Early Learning - 20 minutes. Visual Reception, Fine Motor, Receptive Language, and Expressive Language scales.
- Attention Following trials - 2 minutes
- Brief Observation of Social Communication Change - 13 minutes
- Sensory Processing Assessment - 15 minutes
- Sensory Experiences Questionnaire - 15 minutes (parents only; can be completed online, or in hardcopy form if parents prefer, from location of parent choice)

For children who meet final study eligibility criteria for the intervention trial based on baseline assessment results for the expressive and/or receptive language and sensory reactivity, the study coordinator will complete the written informed consent process at the end of the baseline assessment.

2. The assigned PIE intervention coach for each enrolled family will schedule an initial introductory visit with the family of 45-60 minutes. Topics for discussion will be:

- What do we mean by coaching?
- Why are we doing these sessions?
- How will coaching work?

The coach also will complete the PIE Routines Questionnaire with the parent, as a basis for discussing what the usual family routines are involving the infant, and what goals the parent may have for improving the infant's participation in these routines.

At the end of the session, the coach will record a ~10-minute video of the parent interacting with the infant for use in the first coaching session.

4. Coaching in the first PIE domain for the family (randomly assigned) will take place in 6 weekly visits at the home of the dyad, lasting approximately one hour each. The agenda for each visit will include:

- Check-in and introduction to the session
- Review of selected scenarios in the video of parent-infant interaction from the prior session, to support parents understanding of their infant's level of engagement,

communicative or sensory reactivity cues of the infant and how they are related to the infant's engagement, and how parent's response strategies impact the infant's engagement

- Live coaching - coach will identify with parent what response strategies they will use to try to increase the infant's engagement, provide feedback to the parent during and after their interaction with the infant about what they observe, and elicit parent's reflections on the interaction and how strategies might be changed, expanded or enhanced.
- Family action planning - parent and coach complete a written plan for the coming week of response strategies the parent will consciously use, and the routines in which the response strategies will be used.
- Coach records a ~10-minute video of a parent-infant interaction to use in the next coaching session.

5. Posttest-1 will occur after the conclusion of coaching in the first PIE domain at the study's office in Carrboro, NC. Total estimated time for dyads is 25-30 minutes; parents will spend an additional 15 minutes completing a questionnaire at a location of their choice. The following assessments will be completed:

- Parent-infant interaction session - 20 minutes
- Sensory Experiences Questionnaire - 15 minutes (parents only; can be completed online, or in hardcopy form if parents prefer, from location of parent choice)

6. Coaching in the 2nd PIE domain will take place in 6 weekly visits at the home of the dyads, lasting approximately one hour each.

- Check-in and introduction to the session
- Review of selected scenarios in the video of parent-infant interaction from the prior session, to support parents understanding of their infant's level of engagement, communicative or sensory reactivity cues of the infant and how they are related to the infant's engagement, and how parent's response strategies impact the infant's engagement
- Live coaching - coach will identify with parent what response strategies they will use to try to increase the infant's engagement, provide feedback to the parent during and after their interaction with the infant about what they observe, and elicit parent's reflections on the interaction and how strategies might be changed, expanded or enhanced.
- Family action planning - parent and coach complete a written plan for the coming week of response strategies the parent will consciously use, and the routines in which the response strategies will be used.
- Coach records a ~10-minute video of a parent-infant interaction to use in the next coaching session.

7. Posttest-2 assessments will take place at the study office in Carrboro, NC, and will last approximately 1.25 hours. Parents will also complete two questionnaires requiring an additional ~20 minutes, at the location of their choice.

- Parent-infant interaction session - 20 minutes
- Child-directed speech paradigm - 10 minutes

- Mullen Scales of Early Learning Receptive and Expressive Language Scales - 10 minutes
- Attention Following trials - 2 minutes
- Brief Observation of Social-Communication Change - 13 minutes
- Sensory Processing Assessment - 15 minutes
- Sensory Experiences Questionnaire - 15 minutes (parents only, can be completed online, or in hardcopy form if parents prefer, from location of parent choice)
- PIE Intervention Rating Profile - 5 minutes (parents only, can be completed online, or in hardcopy form if parents prefer, from location of parent choice)

Families will be scheduled for baseline assessments as quickly as possible after the initial screening; we anticipate the study team will have the capacity to schedule and complete baseline assessments within 1 to 2 weeks after receiving the FYIv3.1b; however, family schedule preferences and constraints will be accommodated and may lengthen this time period. The total length of time from the baseline assessment (when they would consent to the intervention trial) through Posttest-2 would be a minimum of 16 weeks, assuming that no visits would be more than one-week apart. However, from our past experience with similar intervention trials, there will be some lengthening of the participation period for most dyads, due to needs to accommodate scheduling conflicts for both assessment and intervention visits. Thus, the total actual length of participation time from the FYIv3.1b completion through Posttest-2 is estimated to average ~22-25 weeks.

6.3.6 End of Study and Follow Up

Coaches will complete an exit interview for the intervention with families at the end of their last coaching session. Parents also will be asked to complete the "Intervention Rating Profile" for the PIE intervention at the time of the Posttest-2 assessment.

At the end of the Posttest-2 assessment, the assessment coordinator (and one or more other assessors as appropriate) will provide information to the family on the child's developmental status based on the standardized assessments conducted, and will provide parents with a written summary that they can take home with them.

Parents who wish to discontinue participating in the intervention will be invited to continue participating in any remaining scheduled assessments. Their reason(s) for discontinuing the intervention will be recorded if the parents is willing to share, and if the reason suggests a possible adverse event, the study coordinator will bring this to the attention of the PIs for review. Similarly, if a parent wishes to withdraw from the entire study, the study coordinator will record the reason if provided, and notify the PIs immediately if the reason indicates a possible adverse event.

Parents will be invited to contact the study coordinator following the end of their study participation if they have questions or concerns related to the study, or if they are seeking assistance in finding community services for their child.

6.3.7 Removal of Subjects

Participants may withdraw voluntarily at any time; this option will be covered in the consent process and study staff will remind parents that they have that option if they express reluctance to continue their study participation at any point.

We do not anticipate any situations in which the study staff would make a decision to remove participants from the study, given the low level of risk associated with the study procedures.

6.4 Statistical Method

6.4.1 Statistical Design

The study is designed as a randomized comparative trial with two phases. For Study Phase 1, dyads will participate in baseline assessments; then eligible, consenting families will be randomized, stratifying by child age, to one of two treatment arms. Arm1 families will participate in initial coaching on the PIE sensory reactivity (SR) domain, and Arm2 families will participate in initial coaching on the PIE prelinguistic communication (PC) domain. Families will participate in 6 weekly coaching sessions in their respective treatment arms, and return for Posttest-1. For Study Phase 2, dyads in Arm1 will receive 6 weekly coaching sessions on the PC domain, and dyads in Arm2 will receive 6 weekly coaching sessions on the SR domain. Then families will return for Posttest-2.

Comparisons of dyads assigned to Arm1 and Arm2 at Posttest-1 will allow us to estimate the separate effects of the two domains of PIE coaching, as dyads will have only been coached in one domain (responding to prelinguistic communication cues or sensory reactivity cues) prior to Posttest-1. At Posttest-2, we will get estimates of the additive effects of coaching in the second PIE domain, and be able to evaluate whether there are any effects of the order of coaching by comparing dyads in Arm1 to those in Arm2.

For analyses, we will utilize repeated measure analyses within a mixed modeling framework, to assess time and tx order effects, while accommodating missing data and optimally utilizing all available data.

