4.1 Hypothesis

This study has four specific objectives, with hypotheses associated with each objective. Understanding the study design will provide context for interpreting the hypotheses. Parent-child dyads will be randomized to one of two study arms. All dyads will receive the full Parents and Infants Engaged (PIE) intervention, but they will be coached on the two PIE domains (prelinguistic communication and sensory reactivity) in different orders. In Arm1, parents will first be coached in responding to their infants' prelinguistic communication cues. In Arm2, parents will first be coached on responding to their infants' prelinguistic communication cues. Posttest-1 assessments will follow the first domain of coaching for all participants. Then parents will be coached in the second domain of PIE, after which dyads will participate in Posttest-2 assessments.

1. Estimate the separate and combined effects of the two PIE intervention domains on dyadic engagement (primary outcome).
 - *H1a:* At Posttest-1, dyads coached in either PIE domain will exhibit moderately more dyadic engagement compared to Baseline (Cohen's $d \geq .40$).
 - *H1b:* At Posttest-2, dyads in both study arms will show additional small to moderate increases in dyadic engagement compared to Posttest-1 (Cohen's $d \geq .25$).
2. Estimate the separate and combined effects of the two PIE intervention domains on infant intentional communication.
 - *H2a:* At Posttest-1, infants in both groups will show no more than modest gains in

- intentional communication (Cohen's $d < .25$).
- *H2b*: At Posttest-2, infants in both groups will show moderate increases in intentional communication compared to Baseline (Cohen's $d \geq .40$).

3. Evaluate the *differential* changes in parent responsiveness following coaching on two individual Parents and Infants Engaged (PIE) intervention domains — responses to variable infant (a) sensory reactivity or (b) prelinguistic communication — as well as *cumulative* changes in parent responsiveness following coaching on both PIE domains.

- *H3a*: At Posttest-1, parents in both intervention arm will show increases in responses attuned to their infants' behaviors compared to Baseline, with parents coached in the sensory reactivity domain showing more responses attuned to infants' sensory reactivity, and parents coached in the prelinguistic communication domain showing more responses attuned to infants' signals of attention focus and communicative intent.

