6.4.3 Planned Analyses

Data will be analyzed using an intention-to-treat analytic approach. Depending on patterns of attrition or numbers of dyads participating in fewer than the planned 6 coaching sessions in each of the two PIE domains, we may additionally employ some post-hoc analytic approaches (e.g., comparisons of treated participants in each arm; including a covariate for number of sessions) to inform our understanding of the outcomes in this proof-of-concept study. The study outcomes based on the planned intention-to-treat analyses will be reported, with supplemental post hoc analyses reported if appropriate/informative.

Analyses will address one primary objective and three secondary objectives:

Primary:

1. Estimate the separate and combined effects of the two PIE intervention domains on dyadic engagement (primary outcome).

Secondary

2. Estimate the separate and combined effects of the two PIE intervention domains on infant intention communication.
3. Evaluate the *differential* changes in parent responsiveness following coaching on two individual Parents and Infants Engaged (PIE) intervention domains — responses to variable infant (a) sensory reactivity or (b) prelinguistic communication — as well as *cumulative* changes in parent responsiveness following coaching on both PIE domains.
4. Determine the extent to which (a) autonomic indices of infant self-regulation and (b) language, sensory reactivity patterns, response to joint attention, and social-communication skills change over the course of the PIE intervention. .

Overall analytic procedures:

All data will be cleaned and inspected for outliers, missing data and distributional irregularities. Although general linear modeling methods are robust to minor violations of distributional assumptions, appreciable departures from normality can compromise statistical tests and estimators. Where error distributions potentially deviate from normality or heteroscedasticity is suspected, the tests of the contrasts described below will be conducted using exact (resampling-based) nonparametric methods.

We will complete planned analyses of study outcomes using repeated measures analyses within a mixed modeling framework, to assess time and tx order effects, while

accommodating missing data and optimally utilizing all available data.

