6.4.3.1 Primary Analyses

The primary objective of this study is to examine whether the novel PIE intervention transforms parent-infant transactions over time as intended, thereby facilitating increases in the time infants spend in dyadic engagement with their parents. We will also evaluate whether dyadic engagement outcomes differ based on whether parents are coached first in the sensory reactivity domain followed by coaching in the prelinguistic communication domain, or are coached in the opposite order.

Specifically, we will estimate the separate and combined effects of the two PIE intervention domains on dyadic engagement (primary outcome). H1a: At Posttest-1, dyads coached in either PIE domain will exhibit moderately more dyadic engagement compared to Baseline (Cohen's $d \geq .40$). H1b: At Posttest-2, dyads in both study arms will show additional small to moderate increases in dyadic engagement compared to Posttest-1 (Cohen's $d \geq .25$).

Our primary analysis will be conducted to explore a priori contrasts of interest within using repeated measures within a mixed modeling framework. Of key interest will be the contrast of Baseline to Posttest-1 scores and the contrast of Baseline to Posttest-2 scores (time effect). In addition, the model will include terms for treatment arm effects and treatment arm-by-time interactions. A time effect will indicate growth in the outcome from baseline to the posttest point, a zero or negligible time effect indicates stability, and a negative time effect suggests a drop in scores. A non-negligible treatment arm effect indicates that the two treatment arms differ on the outcome; while a non-negligible interaction coefficient suggests that the magnitude of change from baseline to the posttest point are not equivalent for members of the 2 treatment arms. Since the primary outcomes are proportions, arc sin transformations of these proportions will be performed before entering them into the models.

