6.4.3.2 Secondary Objectives Analyses, if applicable

Secondary Objective Analyses

Objective 2. Estimate the separate and combined effects of the two PIE intervention domains on infant intention communication.

H2a: At Posttest-1, infants in both groups will show no more than modest gains in intentional communication (Cohen's $d < .25$).

H2b: At Posttest-2, infants in both groups will show moderate increases in intentional communication compared to Baseline (Cohen's $d \geq .40$).

Analyses: This outcome variable involves counts of infant intentional communication attempts. We expect the average number of counts to be sufficiently large (eg. ≥ 8) that a normal approximation to a Poisson error distribution will be appropriate; however, if not, Poisson or negative binomial regression methods, or nonparametric approaches may be employed. The analyses for Objectives 2 and 3 will use the same framework as for our primary Objective #1, that is, to evaluate a priori contrasts of interest within a repeated measures mixed modeling framework. We will examine the contrast of Baseline to Posttest-1 scores and the contrast of Baseline to Posttest-2 scores (time effect). In addition, the models will include terms for treatment arm effects and treatment arm-by-time interactions.

Objective 3. Evaluate the differential changes in parent responsiveness following coaching on two individual Parents and Infants Engaged (PIE) intervention domains — responses to variable infant (a) sensory reactivity or (b) prelinguistic communication — as well as cumulative changes in parent responsiveness following coaching on both PIE domains.

H3a: At Posttest-1, parents in both intervention arm will show increases in responses attuned to their infants' behaviors compared to Baseline, with parents coached in the sensory reactivity domain showing more responses attuned to infants' sensory reactivity, and parents coached in the prelinguistic communication domain showing more responses attuned to infants' signals of attention focus and communicative intent.

H3b: At Posttest-2 (after coaching in both PIE domains), there will be no between-arm differences in parent responses attuned to infant sensory reactions or prelinguistic communication leads, due to increases in parent responsiveness to the newly coached domain of infant behaviors.

Analyses: See analyses for Objective 2.

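### The Posttest-1 arm comparison estimates only the difference between the two PIE domains, and the plan names no arm-specific change for its separate-effects objectives

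*Combined protocol and SAP*

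**What the plan says.** Section 6.4.1 states that comparing Arm 1 with Arm 2 "at Posttest-1 will allow us to estimate the separate effects of the two domains of PIE coaching", and gives the reason: "as dyads will have only been coached in one domain (responding to prelinguistic communication cues or sensory reactivity cues) prior to Posttest-1". Section 4.1 confirms that nobody goes uncoached: "All dyads will receive the full Parents and Infants Engaged (PIE) intervention".

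The primary objective in 6.4.3 is to "Estimate the separate and combined effects of the two PIE intervention domains on dyadic engagement (primary outcome"). Objective 2 has the same form for intentional communication.

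The hypotheses are worded by domain or arm. H1a says that "dyads coached in either PIE domain will exhibit moderately more dyadic engagement compared to Baseline", with d of at least .40. H1b concerns both arms and runs from Posttest-1 to Posttest-2, with d of at least .25. H2b says that "infants in both groups will show moderate increases in intentional communication compared to Baseline".

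For the analysis, 6.4.3.1 says: "Of key interest will be the contrast of Baseline to Posttest-1 scores and the contrast of Baseline to Posttest-2 scores (time effect"). Arm and arm-by-time terms are added to the model, and 6.4.3.2 repeats the scheme. Section 6.4.2 also promises arm-level descriptive results and effect sizes at both posttests. No section names a within-arm change as an estimand, and none states the coding of the time term.

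**The concern.** With two active arms, a between-arm comparison cannot show what either domain does by itself. Section 6.4.1 therefore credits the design with a property it lacks, on the point that Objectives 1 and 2 ask about. A reader who trusts the sentence could take a null arm difference at Posttest-1 as evidence that neither domain has an effect of its own.

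The named key contrast does not clearly fill the gap. If it is an average over arms, a gain can come mostly from one domain and still be reported for both. Sections 3.2 and 6.4.2 say that the effect sizes will guide a larger efficacy trial, so a weak domain could be carried forward unnoticed.

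**Working it through.** **1. The plan's own figures.** Inputs from 6.4.2: 40 dyads (20 per arm), alpha .05, correlations ρ of .3 to .7, power .80. I used a repeated-measures noncentral F with m = 2 time points and 1 and 38 df:

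- arm effect: λ = f²·N·m / (1 + (m−1)ρ)
- time and time-by-arm effects: λ = f²·N·m / (1−ρ)

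| Effect | ρ | Stated f | λ | Power |
|---|---|---|---|---|
| Arm | .3 | .37 | .1369 × 80 / 1.3 = 8.42 | .81 |
| Arm | .7 | .42 | .1764 × 80 / 1.7 = 8.30 | .80 |
| Time, time-by-arm | .3 | .27 | .0729 × 80 / 0.7 = 8.33 | .80 |
| Time, time-by-arm | .7 | .18 | .0324 × 80 / 0.3 = 8.64 | .82 |

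The stated figures reproduce for two time points. None of them concerns a change within one arm.

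**2. What the arm comparison estimates.** Let M be the change that would occur without coaching (maturation, retest), the same in both arms by randomisation. The SR-first arm changes by M + SR and the PC-first arm by M + PC. The arm difference is SR − PC. The arm average is M + (SR + PC)/2. Neither gives SR or PC alone.

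| True change, SR-first / PC-first (SD) | Arm difference | Arm average |
|---|---|---|
| 0 / 0 | 0 | 0 |
| .4 / .4 | 0 | .4 |
| .8 / .8 | 0 | .8 |
| .8 / 0 | .8 | .4 |

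The first three rows share an arm difference of zero. Rows two and four share an average of .4.

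**3. What the planned model can give.** Time and arm-by-time terms together determine each arm's change. In one simulated data set (4,000 dyads; true changes .8 SR-first and 0 PC-first):

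- Reference coding, PC-first as reference: time = .02, interaction = .78. So PC-first = .02 and SR-first = .02 + .78 = .80.
- Sum coding: time = .41, interaction = −.39. So PC-first = .41 − .39 = .02 and SR-first = .41 + .39 = .80.

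Both codings recover both arm changes, but the coefficient called time is .02 under one and .41 under the other.

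**4. Precision of arm-specific changes.** Assumption: d is in raw-SD units, since the documents do not define its denominator. SE = √(2(1−r)/n), half-width = 2.024 × SE (38 df), two-sided alpha .05. At r = .5, SE is √(1/20) = .224 per arm and √(1/40) = .158 averaged.

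| r | Half-width per arm | Half-width averaged | Power for d = .40 per arm | Power for d = .40 averaged |
|---|---|---|---|---|
| .3 | .54 | .38 | .31 | .55 |
| .5 | .45 | .32 | .41 | .69 |
| .7 | .35 | .25 | .61 | .89 |

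**5. How often an averaged contrast could mislead.** This is an illustration only; the true changes below come from no document. With changes of .60 and .20, 20 per arm and r = .5, the averaged contrast is significant in 69% of simulated trials and the interaction in 24%. In 53% the average is significant and the interaction is not (44% at r = .3, 57% at r = .7). With .80 and 0 at r = .5, that last outcome occurs in 21%. In 46% the averaged d reaches .40 while the weaker arm's observed change does not.

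**The case against.** A reader might infer that nothing planned can address H1a. The documents do not support that. H1a is a change from Baseline, the planned terms jointly give each arm's change (step 3), and 6.4.2 promises arm-level descriptive results and effect sizes, which it ranks above the statistical comparisons. The interaction test is therefore not the only protection.

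A reader might also infer that the key contrast pools the arms. That is one possible coding, and the plan states none. H1a can moreover be read as covering all dyads whichever domain came first, in which case an averaged contrast answers it directly. H1b and H2, which speak of both arms or groups, fit that reading less well, and the separate-effects part of Objectives 1 and 2 would still lack a named contrast.

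Section 6.4.3.1 interprets the arm and interaction terms correctly and nowhere says that a null arm difference means no effect. Section 6.2.1 says that efficacy is not an aim and that the necessary controls are absent. Both points stand, but neither withdraws the claim in 6.4.1. The arm comparison does suit Objective 3, which asks about differential change in parent responsiveness; the problem is the broader claim.

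**Conclusion.** The sentence in 6.4.1 is wrong as written: the Posttest-1 arm comparison estimates SR minus PC and nothing more. This follows from the design and needs no numerical assumption. Beyond that, the fault is one of specification. The model can deliver arm-specific changes, but the plan neither names them nor fixes the meaning of its key contrast.

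How far this could mislead depends on the coding and on how unequal the domains are. The percentages in step 5 assume an averaged contrast, raw-SD units and chosen true changes, and do not forecast this trial. Even arm-specific changes would include maturation and retest, so they would not be causal effects of a domain. The point deserves correction because it bears on the primary objective and costs little to repair.

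**What to change.** 1. Reconcile the arm labels first. The Synopsis (General Design Description) and 6.4.1 put SR first in Arm 1; 5.1 and 6.1.2 put PC first. Section 4.1 describes both arms as starting with PC.
2. In 6.4.1, say that the Posttest-1 comparison estimates the difference between initial SR coaching and initial PC coaching, and that a null difference does not show either domain to be ineffective.
3. In 6.4.3.1 and 6.4.3.2, state the coding and prespecify arm-specific changes with 95% intervals from the same model: Baseline to Posttest-1 for H1a and H2a, Posttest-1 to Posttest-2 for H1b, and Baseline to Posttest-2 for H2b. Keep the arm-averaged time contrast as a summary.
4. Describe these as before-after changes that include maturation and retest, and reword Objectives 1 and 2 to match.

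I would not add a rule that each arm must reach its threshold. If both true changes were exactly .40, each estimate would reach .40 about half the time, so both would in only .5 × .5 = 25% of trials. That sits badly with the priority that 6.4.3 gives to avoiding type II errors.

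The change needs wording and a few extra contrasts from a model already planned, with no new data. The price is the wider intervals and lower power in step 4.
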